3.1 Treatment Cohort

Table 3-1 Study VX14-661-110: Treatment Cohort

Event/Assessment ^a	Day -28 to Day -1	Treatment Period ^b						ETT Visit/ Departing Visit (Within 7 Days of Last Dose of Study Drug) ^{b,c,d,e}	Safety Follow-up Visit 28 (± 7) Days After Last Dose ^{c,d,e}
		Day 1 ^f / Returning Visit ^{b,g}	Day 15 (± 3 days)	Weeks 8, 16, 24, 36 (± 5 days)	Week 48 (± 5 days)	Weeks 60, 72, 84 (± 5 days)	Week 96 (± 5 days)		
Clinic visit		X	X	X	X	X	X	X	X

^a All assessments will be performed before dosing unless noted otherwise.

^b Selected visits may overlap with visits in the other qualified Vertex study: the Screening Visit of the other qualified Vertex study and a scheduled Treatment Period visit; the last required visit of the other qualified Vertex study and the Returning Visit; and the visit with the first dose of study drug in the other qualified Vertex study and the ETT Visit (refer to [Section 8.1.1.1](#) and [Section 8.1.1.3](#) for the timing/order of assessments in these cases).

^c If the subject prematurely discontinues study treatment, an ETT Visit should be scheduled as soon as possible after the subject decides to terminate study treatment ([Section 8.1.1.3](#)). Subjects who prematurely discontinue treatment will also be required to complete the Safety Follow-up Visit, approximately 28 (± 7) days after their last dose of study drug. If the ETT Visit occurs 3 weeks or later following the last dose of study drug, then the ETT Visit will replace the Safety Follow-up Visit, and a separate Safety Follow-up Visit will not be required.

^d If a subject is continuing onto commercially available VX-661/ivacaftor, the ETT Visit ([Section 8.1.1.3](#)) will be completed before dosing with commercial drug begins, and the Safety Follow-up Visit ([Section 8.1.1.2](#)) will not be required.

^e If a subject discontinues treatment to participate in another qualified Vertex study, the ETT Visit ([Section 8.1.1.3](#)) will be completed, and the Safety Follow-up Visit ([Section 8.1.1.2](#)) will not be required if the subject enrolls in the other study within 28 (± 7) days of the last dose of study drug in Study VX14-661-110.

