8.1.1.2 Safety Follow-up

Treatment Cohort

Subjects who do not complete the Day 1 Visit in Study VX14-661-110 within 28 days after the last dose of study drug in the parent study are to complete the Safety Follow-Up Visit in the parent study before receiving the first dose of study drug in Study VX14-661-110.

The Safety Follow-up Visit is scheduled to occur 28 (\pm 7) days after the last dose of study drug. The Safety Follow-up Visit assessments are listed in [Table 3-1](#).

If a subject is continuing onto commercially available VX-661/ivacaftor, the Early Treatment Termination Visit ([Section 8.1.1.3](#)) will be completed before dosing with commercial drug begins, and the Safety Follow-up Visit will not be required.

If a subject discontinues treatment to participate in another qualified Vertex study, the Early Treatment Termination Visit ([Section 8.1.1.3](#)) will be completed, and the Safety Follow-up Visit will not be required if the subjects enrolls in the other study within 28 (\pm 7) days of the last dose of study drug in Study VX14-661-110.

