8.1.1.3 Early Treatment Termination

Treatment Cohort

If a subject prematurely discontinues study treatment, an Early Treatment Termination Visit should be scheduled as soon as possible after the subject decides to terminate study treatment and should occur within 7 days after the last dose of study drug. Subjects who prematurely discontinue treatment will also be required to complete the Safety Follow-up Visit, approximately 28 (\pm 7) days after their last dose of study drug as described in [Section 8.1.1.2](#). The assessments performed at the Safety Follow-up Visit are listed in [Table 3-1](#).

If the Early Treatment Termination Visit occurs 3 weeks or later following the last dose of study drug, then the Early Treatment Termination Visit will replace the Safety Follow-up Visit, and a separate Safety Follow-up Visit will not be required. If a subject discontinues Study VX14-661-110 to participate in another qualified Vertex study, and the subject does not re-enroll in Study VX14-661-110, the Early Treatment Termination Visit will replace the Safety Follow-up Visit, and a separate Safety Follow-up Visit will not be required.

During the course of study conduct, if VX-661 in combination with ivacaftor is approved and available for the treatment of CF in populations enrolled in Study VX14-661-110, subjects with

the approved *CFTR* genotypes may be discontinued from this rollover study at the discretion of the sponsor (Section 10.6). If a subject is continuing onto commercially available VX-661/ivacaftor, the Early Treatment Termination Visit will be completed before dosing with commercial drug begins, and the Safety Follow-up Visit (Section 8.1.1.2) will not be required. Alternatively, if local health authorities decline to approve, or if clinical benefit is not demonstrated for the use of VX-661 in combination with ivacaftor for the treatment of CF in populations enrolled in Study VX14-661-110, subjects with the relevant *CFTR* genotypes may be discontinued after communication to investigators and IRBs/IECs of the risks/benefits related to the safety and efficacy observed for the subset of subjects. If subjects are discontinued from the study, an Early Treatment Termination Visit should occur within 7 days of the last dose of study drug and a Safety Follow-up Visit should occur within 28 (\pm 7) days after the last dose of study drug.

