Note: Subjects who permanently discontinue study drug treatment during the parent study, including at the last visit of the Treatment Period are not eligible to enroll into the Treatment Cohort.

3. Willing to remain on a stable CF medication (and supplement) regimen through the Safety Follow-up Visit of Study VX14-661-110.
- Subjects **re-enrolling in the Treatment Cohort** must meet all of the following criteria:
 1. Previously received at least 4 weeks of study drug before discontinuing Study VX14-661-110 to participate in another qualified Vertex study, which is defined as a Vertex study of investigational CFTR modulators that allows participation of subjects in Study VX14-661-110. Note: other qualified Vertex studies do not include studies of lumacaftor in combination with ivacaftor or ivacaftor monotherapy.
 2. Completed the last required visit of another qualified Vertex study before or during the Returning Visit in Study VX14-661-110. (If the last required visit of the other qualified Vertex study is more than 60 days from the Returning Visit in Study VX14-661-110, approval of the medical monitor is required.) Subjects who discontinue Study VX14-661-110 to screen for another qualified Vertex study, and do not enroll into the other study, are eligible to re-enroll in Study VX14-661-110.
 3. Willing to remain on a stable CF medication (and supplement) regimen through the Safety Follow-up Visit of Study VX14-661-110.
 4. Subjects who discontinue Study VX14-661-110 more than once to participate in another qualified Vertex study may not re-enroll in Study VX14-661-110 a second time.
 - Subjects entering the **Observational Cohort** must meet the following criteria:
 1. <18 years of age (age on the date of informed consent/assent in the parent study)
 2. Completed study drug treatment during the Treatment Period in a parent study (Studies VX13-661-103, VX14-661-106, VX14-661-107, VX14-661-108, or VX14-661-109), study drug treatment and the Safety Follow-up Visit for subjects from Study VX14-661-111, or study drug treatment and follow-up as specified in other parent Vertex studies investigating VX-661 in combination with ivacaftor, but do not elect to enroll in the Study VX14-661-110 Treatment Cohort (note: Studies VX11-661-101, and VX15-661-113 are not eligible parent studies); or

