9.5 Removal of Subjects (Treatment Cohort)

Subjects may withdraw from the study at any time at their own request. Subjects may be withdrawn from study drug treatment at any time at the discretion of the investigator or Vertex for safety, behavior, noncompliance with study procedures, or administrative reasons. If a subject has been withdrawn from study drug treatment, the subject will continue to be followed, provided the subject has not withdrawn consent.

Subjects who discontinue study treatment early should continue to return for study assessments at the Early Treatment Termination Visit and/or the Safety Follow-up Visit, as noted in [Section 8.1.1.3](#).

If a subject does not return for a scheduled visit, reasonable effort will be made to contact the subject. In any circumstance, reasonable effort will be made to document subject outcome. The investigator will inquire about the reason for withdrawal, request that the subject return all unused investigational product(s), request that the subject return for a Safety Follow-up Visit, if applicable (see [Section 8.1.1.2](#)), and follow up with the subject regarding any unresolved AEs.

If the subject withdraws consent for the study, no further evaluations will be performed and no additional data will be collected. Vertex may retain and continue to use any data collected before such withdrawal of consent.

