11.8.6 Liver Function Test Parameters (Treatment Cohort)

Liver Function Testing

Liver function testing (ALT, AST, GGT, ALP, direct bilirubin, and total bilirubin) must be performed as noted for serum chemistry, while subjects are receiving study drug treatment and at the Early Treatment Termination Visit and the Safety Follow-up Visit. These blood samples should be processed and shipped immediately per the Laboratory Manual.

Subjects with new treatment-emergent ALT or AST elevations of $>3 \times \text{ULN}$ and clinical symptoms must be followed closely, including repeat confirmatory testing performed by the central laboratory within 48 to 72 hours of the initial finding and subsequent close monitoring of ALT and AST levels, as clinically indicated. In addition, if ALT or AST is $>5 \times \text{ULN}$, repeat follow-up levels must be obtained within 7 ± 2 days.

If a subject cannot return to the site for liver function testing, a local laboratory may be used. Elevations in LFTs at the local laboratory must be reported immediately to the medical monitor, and the subject must have the tests repeated and sent to the central laboratory as soon as possible (ideally within 48 to 72 hours).

Study Drug Interruption

Study drug administration **must be interrupted** immediately (prior to confirmatory testing), and the medical monitor must be notified, if any of the following criteria is met:

- ALT or AST $>8 \times \text{ULN}$
- ALT or AST $>5 \times \text{ULN}$ for more than 2 weeks
- ALT or AST $>3 \times \text{ULN}$, in association with total bilirubin $>2 \times \text{ULN}$ and/or clinical jaundice

A thorough investigation of potential causes should be conducted, and the subject should be followed closely for clinical progression.

If no convincing alternative etiology (e.g., acetaminophen use, viral hepatitis, or alcohol ingestion) for the confirmed elevated transaminases is identified, regardless of whether ALT or AST levels have improved, study drug treatment must be permanently discontinued if repeat testing within 48 to 72 hours confirms the initial elevation. Subjects in whom treatment is discontinued for elevated transaminases should have their transaminases monitored closely until levels normalize or return to baseline.

Resumption of Study Drug

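### Protocol 8.1.1.3 waives the Safety Follow-up Visit without the enrolment deadline in 8.1.1.2 and Table 3-1 footnote e, so a small group of leavers falls under two different rules

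*Protocol*

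**What the plan says.** Days below are counted from the last dose of study drug (Day 0).

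- **Default.** Protocol 8.1.1.3 and Table 3-1 footnote c require a subject who stops treatment early to attend an ETT Visit, which should fall within 7 days of the last dose, and a Safety Follow-up Visit at 28 (±7) days. Section 8.1.1.3 refers to 8.1.1.2 for the latter.
- **Late ETT Visit.** Both places let an ETT Visit held 3 weeks or later stand in for the Safety Follow-up Visit.
- **Waiver in 8.1.1.2 and footnote e.** For a subject leaving for another qualified Vertex study, 8.1.1.2 says that "the Safety Follow-up Visit will not be required if the subjects enrolls in the other study within 28" (±7) days of the last dose. Footnote e agrees: the visit "will not be required if the subject enrolls in the other study within 28 (± 7) days of the last dose".
- **Waiver in 8.1.1.3.** If a subject leaves to take part in another qualified study "and the subject does not re-enroll in Study VX14-661-110, the Early Treatment Termination Visit will replace the Safety Follow-up Visit". This sentence has no time limit and does not ask whether the subject has enrolled in the other study.
- **Section 9.5.** Early discontinuers should return for the "Early Treatment Termination Visit and/or the Safety Follow-up Visit, as noted in" 8.1.1.3. A later sentence has the investigator "request that the subject return for a Safety Follow-up Visit, if applicable" and points to 8.1.1.2.
- **Section 9.1.** The re-enrolment criteria foresee "Subjects who discontinue Study VX14-661-110 to screen for another qualified Vertex study, and do not enroll into the other study" and let these subjects come back. For those who did join another study, if its last required visit is "more than 60 days from the Returning Visit in Study VX14-661-110, approval of the medical monitor is required".
- **Section 11.8.6.** Liver function tests must be done while "subjects are receiving study drug treatment and at the Early Treatment Termination Visit and the Safety Follow-up Visit".

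**The concern.** Two sections decide whether the same visit takes place, and they use different tests. One asks whether the subject has entered the other study by about Day 35, which a site can establish in time. The other asks whether the subject will ever come back to Study 110, which a site generally cannot know by Day 35. Section 9.5 cites both sections and does not choose between them.

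The enrolment deadline appears to serve a purpose: a subject who moves promptly into another study comes under that study's monitoring. A subject who has stopped drug and is not yet enrolled elsewhere may be under no study's monitoring. For that subject, 8.1.1.3 removes the one scheduled off-drug assessment. In Table 3-1 that visit carries hematology, coagulation, chemistry (with liver tests), lipids, vitamins, urinalysis, ECG, vital signs, pulse oximetry, spirometry and a serum pregnancy test for females of childbearing potential. For subjects under 18 it is also the latest date for an eye examination not done at the ETT Visit (footnote o). Safety is the primary objective, so the rule should be clear.

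**Working it through.** The plan gives no figure to reproduce. The check compares the rules case by case and then works out the visit windows.

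**Step 1: apply each rule.** Cases A to D assume an ETT Visit before 3 weeks.

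| Case | 8.1.1.2 and footnote e | 8.1.1.3 | Result |
|---|---|---|---|
| A. Enrols elsewhere by Day 35, never returns | Waived | Waived | Agree |
| B. Enrols elsewhere by Day 35, later returns | Waived | Own waiver not met, but its default refers to 8.1.1.2, which waives | Agree |
| C. Not enrolled elsewhere by Day 35, never returns | Not waived; default visit stands | Waived | **Diverge** |
| D. Not enrolled elsewhere by Day 35, later returns | Not waived | Not waived | Agree |
| E. ETT Visit at 3 weeks or later | Replaced (footnote c) | Replaced | Agree |

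Only case C diverges. C and D differ only in whether the subject eventually returns. A late enroller must complete the other study's last required visit before or at the Returning Visit (9.1), so any return comes after Day 35. A subject who left only to screen has no stated time limit for returning. The exception is a subject who has already used the single permitted re-enrolment (exclusion criterion 8), for whom non-return is known.

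**Step 2: who is in case C.** Late enrollers are. Subjects who left only to screen are included only if leaving to participate is read to cover leaving to screen. Section 9.1 uses the two phrases separately, and the 8.1.1.3 waiver uses only the first, so they are probably outside it.

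**Step 3: how much earlier the last assessment falls.** Inputs: ETT Visit on Day 0 to 7 if on time; Safety Follow-up Visit window 28 − 7 = Day 21 to 28 + 7 = Day 35.

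- On-time ETT Visit: minimum 21 − 7 = 14 days; maximum 35 − 0 = 35 days.
- Against nominal Day 28: 28 − 7 = 21 to 28 − 0 = 28 days.
- Late ETT Visit, for example Day 20: 21 − 20 = 1 to 35 − 20 = 15 days.
- ETT Visit on Day 21 or later: no loss, because it replaces the visit.

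**Step 4: adverse event collection.** For subjects without a Safety Follow-up Visit, 13.1.1.3 ends collection at the earliest of several points. One is 28 days after the last dose. Another is an ETT Visit at 3 weeks or later. The third bullet names the ETT Visit or enrolment in another qualified study. If that bullet ended collection at any ETT Visit, the 3-week bullet would be redundant. Read so that every bullet has effect, collection for a case C subject runs to Day 28. The treatment-emergent period for subjects without the visit also ends at Day 28 (Protocol 12.3.1, SAP 9.1). Days lost: 28 − 28 = 0.

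**Step 5: scale.** The documents give no count. Purely as an assumption, 1 to 10 subjects out of the 1,044 in SAP 6.2 would be 1/1,044 = 0.1% to 10/1,044 = 1.0%.

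**The case against.** **The waivers may be alternatives.** Section 8.1.1.2 and footnote e say if, not only if, so either waiver might be sufficient. The word only is indeed an inference. But on this reading the deadline does nothing for anyone who never returns, and matters only for subjects who later come back. The wording would still need repair.

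**The site will fall back on the stricter rule.** The default in 8.1.1.3 points to 8.1.1.2, and a site that cannot confirm non-return should hold the visit. This is a fair mitigation. It depends on each site resolving the texts in the same way, and 9.5 does not help it.

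**The group is small.** This stands. Subjects may screen while still in the Treatment Cohort (8.1.1.1), and the ETT Visit may coincide with the first dose in the other study (8.1.1.3), so the ordinary route leaves no gap. A late enroller whose ETT Visit is held on that day is past 3 weeks, and the visit is replaced under a rule nobody disputes.

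**Other safeguards remain.** This also stands. The ETT Visit supplies a full set of laboratory, ECG and vital sign data. Unresolved adverse events are followed up (9.5), and later related serious events stay reportable (13.1.2.2). Subjects taken off drug for raised transaminases or QTc are monitored until values normalise or return to baseline (11.8.6, 11.8.4). The eye examination for under-18s is still owed and may be done at the ETT Visit. None of these schedules an off-drug check for a subject who was well at the ETT Visit.

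**Conclusion.** The point holds as a minor inconsistency with a patient-safety side. The rules diverge for subjects not enrolled elsewhere by about Day 35 who never return and whose ETT Visit was before 3 weeks. Under 8.1.1.3 they miss the off-drug assessment. Their last assessment falls 14 to 35 days earlier if the ETT Visit was on time, and as little as 1 day earlier if it was on Day 20.

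A reader might infer three stronger things that the documents do not support:

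- **Adverse event collection stops at the ETT Visit, losing 21 to 28 of 28 days.** That needs a reading of 13.1.1.3 which makes its 3-week bullet redundant.
- **Every subject who fails screening elsewhere is affected.** The waiver covers leaving to participate, and 9.1 treats leaving to screen as a separate matter.
- **The primary safety analysis is compromised.** No endpoint, analysis set or period end date changes, and pooled descriptive summaries are unlikely to move.

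The conclusion assumes that the early-discontinuation default applies unless a waiver is met. The number affected is unknown and probably small.

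**What to change.** In 8.1.1.3, replace the re-enrolment condition so that the visit is waived if the subject enrols in the other study within 28 (±7) days of the last dose, matching 8.1.1.2 and footnote e. Add that leavers not enrolled by then, including those who left to screen and did not enrol, complete the Safety Follow-up Visit unless their ETT Visit was 3 weeks or later after the last dose.

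Optionally, clarify in 13.1.1.3 that the third bullet applies to subjects who enrol in another qualified Vertex study. This only tidies the wording. Section 9.5 and the SAP's treatment-emergent period need no change.

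The cost is an edit to one sentence, one added sentence, and a few additional follow-up visits, which 8.1.1.2 and footnote e already leave in place for late enrollers.

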8.1.2 Observational Cohort (Eligible Subjects <18 Years of Age)

8.1.2.1 Day 1

Following consent and assent (where applicable) and confirmation of eligibility, subjects will undergo the Day 1 assessments as shown in Table 3-2.

Timing of Day 1 Visit in Study VX14-661-110 Active Sites

The Day 1 Visit of the Observational Cohort will be on the **same day** as the last scheduled visit of the parent study for subjects at Study VX14-661-110 sites that have been activated by the time the last scheduled visit of the parent study has been completed. Subjects at these active sites MAY have to repeat any Study VX14-661-110 Day 1 assessments that were specified to be performed at the last scheduled study visit of the parent study. Assessments for the Observational Cohort are listed in Table 3-2.

Timing of Day 1 Visit in Study VX14-661-110 Nonactive Sites

The Day 1 Visit of the Observational Cohort of Study VX14-661-110 **will NOT coincide** with the last scheduled visit of the parent study for subjects at Study VX14-661-110 sites that have NOT been activated by the time the last scheduled visit of the parent study has been completed. Subjects at these nonactive sites will have to repeat any Study VX14-661-110 Day 1 assessments that were specified to be performed at the last scheduled visit of the parent study. Assessments for the Observational Cohort are listed in Table 3-2.

8.1.2.2 Long-term Follow-up

Subjects will be followed for approximately 2 years. A telephone contact will be made approximately every 3 to 4 months during the first year and at approximately 2 years (\pm 4 weeks) as shown in [Table 3-2](#).

8.1.3 Lost to Follow-up

A subject will be considered lost to follow-up if both of the following occur:

- The subject misses 2 consecutive study visits (telephone contact and/or clinic visit) and is subsequently unable to be contacted by telephone (3 documented attempts by telephone within 2 weeks following the second missed visit)
- The subject does not respond within 2 weeks to a registered letter sent after the 3 attempted telephone contacts.

8.2 Rationale for Study Design and Study Drug Regimens

8.2.1 Study Design

The *F508del-CFTR* mutation is the most prevalent of the *CFTR* mutations. In vitro studies in primary cultures of HBE from subjects with CF who are homozygous for the *F508del-CFTR* mutation have demonstrated significant increases in CFTR activity with the addition of VX-661 in combination with ivacaftor when compared to no treatment, VX-661 alone, or ivacaftor alone. Clinical studies of subjects with CF have demonstrated significant increases in lung function (FEV₁) in subjects with CF who are homozygous or heterozygous for the *F508del-CFTR* mutation when treated with VX-661 in combination with ivacaftor when compared to placebo (Study VX11-661-101).¹⁸ Four Phase 3 studies are investigating the efficacy and safety of VX-661 in combination with ivacaftor in subjects with CF who are homozygous (Study VX14-661-106) or heterozygous (Studies VX14-661-107, VX14-661-108, and VX14-661-109) with *F508del-CFTR* mutation. Study VX14-661-107 was terminated early because the study met the prespecified futility criteria. In addition, 3 Phase 2 studies are investigating the safety and efficacy of VX-661 in combination with ivacaftor in subjects with CF who are homozygous for *F508del-CFTR* (Study VX13-661-103, Study VX14-661-111, and Study VX15-661-112). Study VX16-661-114 is a Phase 3b study being conducted in subjects with CF who are homozygous for *F508del*.

Study VX14-661-110 will enroll subjects with CF who participated in a qualifying parent study of VX-661 in combination with ivacaftor (Studies VX13-661-103, VX14-661-106, VX14-661-107, VX14-661-108, VX14-661-109, VX14-661-111, and other eligible Vertex studies investigating VX-661 in combination with ivacaftor). Study VX14-661-110 will enroll subjects with CF who participated in a qualifying parent study (Studies VX15-661-112, VX16-661-114, and other eligible Vertex studies investigating VX-661 in combination with ivacaftor) or who completed study drug treatment.

Results from Study VX14-661-110 will provide information on the safety and efficacy of long-term treatment with VX-661 in combination ivacaftor in subjects with CF who are aged 12 years and older and homozygous or heterozygous for the *F508del-CFTR* mutation. Study VX14-661-110 offers an opportunity to continue treatment with VX-661 in combination with ivacaftor for subjects in qualifying parent studies who had completed their assigned treatment with combination therapy. For subjects who received placebo in their qualifying parent study,

Study VX14-661-110 offers the opportunity to receive treatment with VX-661 in combination with ivacaftor. For subjects <18 years of age (age on the date of informed consent/assent in the parent study) not eligible for further treatment with VX-661 and ivacaftor or who choose not to continue treatment, participation in the Observational Cohort of this study provides an opportunity for long-term safety data collection after subjects discontinue VX-661 in combination with ivacaftor in an eligible parent study.

If an evaluation of the efficacy data from the Phase 3 studies suggests that the VX-661/ivacaftor treatment does not provide clinically meaningful benefit for subsets of subjects included in these studies, Vertex may recommend that subjects with relevant genotypes discontinue from the Treatment Cohort. In addition, if local health authorities decline to approve, or if clinical benefit is not demonstrated for the use of VX-661 in combination with ivacaftor for the treatment of CF in populations enrolled in Study VX14-661-110, subjects with the relevant *CFTR* genotypes may be discontinued after communication to investigators and IRBs/IECs of the risks/benefits related to the safety and efficacy observed for the subset of subjects.

